8.2.3 Supportive analyses of the secondary efficacy variables

As mentioned in [Table 7–2](#), the supportive analyses for all secondary variables will be performed using the modified composite estimand for binary variables (using MI-MCMC/monotone regression as in [Section 8.1.4.3](#)) and on OC.

For PASI90, the MI will be run on the PASI score on subjects involving at least 3% of BSA at Baseline.

For the MDA (and VLDA) MI analysis, subjects with BSA <3 at Baseline will always meet the criteria $PASI \leq 1$ or $BSA \leq 3$ except in the cases where a BSA score >3 is observed. Subjects involving at least 3% of BSA at Baseline will have their BSA values imputed using MI when deriving MDA (VLDA).

Additionally, subgroup analyses will be performed on the PASI90 response at Week 16 (in subjects with PSO involving at least 3% of BSA at Baseline) endpoint. Refer to [Section 4.8](#) for the list of subgroups of interest. The same analysis method than the one used for the subgroup analysis of the primary endpoint will be performed. The results will be presented similarly.

To assess the impact of the COVID-19 pandemic, the analysis of secondary efficacy endpoints will be repeated on the COVID-19-free Set using the primary analysis method.

8.3 Statistical analysis of other efficacy variables

8.3.1 Derivation of other efficacy variables

The analysis of other efficacy variables will be performed in the two randomized treatment groups.

8.3.1.1 Time to ACR20, ACR50, ACR70 response from Baseline

Time to a given response will be defined as the length in days from Baseline until the first date when the response is achieved.

Time from Baseline to censoring will be considered for the following subjects:

- Subjects who discontinue study treatment prior to achieving a response will be censored at the date of study treatment discontinuation.
- Subjects who reach the end of treatment period visit without achieving the given response will be censored at the date of the end of treatment period visit (for the interim analysis, subjects who reached Week 16 without achieving the given response will be censored at that visit).

8.3.1.2 ACR20, ACR50 and ACR70 response

Method for derivation of ACR50 can be found in [Section 8.1.1](#). ACR20 and ACR70 will be derived similarly except that they will be based on a 20% and on 70% improvement from Baseline.

ACR20, ACR50 and ACR70 responses will be analyzed at Week 4, 8, 12, and 16.

8.3.1.3 PASI75, PASI90, and PASI100 response (in subjects with PSO involving at least 3% of BSA at Baseline)

Method for derivation of PASI score can be found in [Section 8.2.1.2](#).

PASI75, PASI90, and PASI100 are binary variables equal to 1 if the percentage improvement from Baseline in the PASI scores is $\geq 75\%$, $\geq 90\%$, 100% and 0 if the percentage improvement from Baseline is $< 75\%$, 90%, 100% respectively.

For PASI75, PASI90, and PASI100, the PASI score and the change from Baseline for subjects with PSO involving at least 3% of BSA at Baseline will be analyzed at Week 4, 8, 12 and 16.

8.3.1.4 Composite endpoints composed of ACR50/PASI90 and ACR50/PASI100 response (in subjects with PSO involving at least 3% of BSA at Baseline)

Composite endpoint composed of ACR50 and PASI90 is a binary variable equal to 1 for subjects responding to both ACR50 (ACR50=1) and PASI90 (PASI90=1).

The composite endpoint will be equal to 0 if ACR50=0 or PASI90=0 regardless of whether any of the two endpoints is missing.

The same rules as above will be applicable for the composite endpoint between ACR50 and PASI100.

The composite endpoints will be missing if both endpoints are missing or if any of the two is missing and the other one equal to 1. Each endpoint (ACR50 and PASI90 or PASI100) will be imputed separately before deriving the composite endpoint. The composite endpoints for subjects with PSO involving at least 3% BSA at Baseline will be analyzed at Week 4, 8, 12 and 16.

8.3.1.5 Proportion of Psoriatic Arthritis Response Criteria (PsARC) responders

The PsARC is based on the TJC (68 joints) and SJC (66 joints), the PGA-PSA and PhGA-PSA.

The PsARC response is defined as improvement from Baseline in at least 2 of the 4 measures (TJC, SJC, PGA-PSA, PhGA-PSA) 1 of which must be TJC or SJC and no worsening from Baseline in any of the 4 measures:

- improvement for TJC and SJC is defined as a reduction of $\geq 30\%$. Improvement of PGA-PSA and PhGA-PSA is defined as a reduction of the 100-point VAS of ≥ 20 points and, worsening is defined as an increase of and,
- worsening for TJC and SJC is defined as an increase of $\geq 30\%$. Worsening for PGA-PsA and PhGA-PsA is defined as an increase of the 100-point VAS of ≥ 20 .

PsARC response will be analyzed at Week 4, 8, 12, and 16.

8.3.1.6 Psoriatic Arthritis Disease Activity Score (PASDAS) categories

The PASDAS is a composite score that includes patient and physician global scores of skin and joint disease, SJC, TJC, LEI, tender dactylitis count (sum of tenderness scores), the physical component of the SF-36 Health Survey, and level of hs-CRP. PASDAS is calculated using the following equation:

$$\begin{aligned} \text{PASDAS} = & \left((0.18 \times \sqrt{\text{Physician global VAS}}) + (0.159 \times \sqrt{\text{Patient global VAS}}) \right. \\ & - (0.253 \times \sqrt{\text{SF36 PCS}}) + (0.101 \times \text{LN}(\text{SJC} + 1)) + (0.048 \times \text{LN}(\text{TJC} + 1)) \\ & + (0.23 \times \text{LN}(\text{LEI} + 1)) + (0.377 \times \text{LN}(\text{Tender dactylitis count} + 1)) \\ & \left. + (0.102 \times \text{LN}(\text{hs} - \text{CRP} + 1) + 2) \right) \times 1.5 \end{aligned}$$

Note: LN=natural logarithm

If Tender Dactylitis count is missing because LDI=0 at Baseline, Tender Dactylitis count will be replaced by 0 in the formula.

If for any other reason a PASDAS component is missing, PASDAS will be set to missing.

The following categories are used to define the level of disease activity:

- Remission: PASDAS ≤ 1.9
- Low disease activity: PASDAS > 1.9 to < 3.2
- Moderate disease activity: PASDAS 3.2 to < 5.4
- High disease activity: PASDAS ≥ 5.4

The PASDAS categories and the change from Baseline in PASDAS score will be analyzed at Week 4, 12, and 16.

8.3.1.7 MDA response

Method for derivation of the MDA response can be found in [Section 8.2.1.4](#).

MDA response will be analyzed at Week 4, 8, 12, and 16.

8.3.1.8 Very Low Disease Activity (VLDA) response

Like MDA, VLDA is a state of disease activity deemed a useful target of treatment by both the subject and physician, given current treatment possibilities and limitations.

A subject is considered as having VLDA if all 7 of the criteria used for MDA and listed in [Section 8.2.1.4](#) are fulfilled. If any of the 7 criteria is not met, then the subject is considered as non-responder.

VLDA response will be analyzed at Week 4, 8, 12 and 16.

8.3.1.9 Proportion of subjects with an IGA score of 0 (clear) or 1 (almost clear) AND at least a 2-grade reduction from Baseline in the subset of subjects with psoriatic skin lesions at Baseline

Method for derivation of this variable can be found in [Section 8.2.1.6](#).

The proportion of subjects with an IGA score of 0 (clear) or 1 (almost clear) AND at least a 2-grade reduction from Baseline in the subset of subjects with psoriatic skin lesions at Baseline will be analyzed at Week 4, 8, 12 and 16.

For some subjects with BSA $\geq 3\%$ at Baseline, IGA data have not been captured at some post-Baseline visits when BSA $< 3\%$ at those visits. To address that, an additional supportive analysis will be performed in which these subjects will be considered as IGA responders at the respective visit.

In this context of this analysis, observed data for % of BSA affected by PSO will also be analyzed by visit using descriptive statistics.

8.3.1.10 Disease Activity Index for Psoriatic Arthritis (DAPSA) score categories, state and change from Baseline in DAPSA score

Disease Activity Index for Psoriatic Arthritis is a composite score of patient global and pain VAS, TJC, SJC and hs-CRP that incorporates a pattern of peripheral arthritis that often is encountered in PsA. DAPSA score will be calculated as follows:

$$DAPSA = SJC + TJC + PGA - Arthritis (VAS) + PtAAP (VAS) + hs - CRP$$

where:

- SJC ranges from 0 to 66
- TJC ranges from 0 to 68
- PGA-Arthritis represents the patient's global assessment of arthritis ranging from 0 to 10; 0=best, 10=worst (using the unrounded VAS that ranges from 0 to 100 mm and dividing this value by 10) (Refer to [Section 8.3.1.24](#)).
- PtAAP VAS ranges from 0 to 10 0=best, 10=worst (unrounded, by dividing the original value by 10)
- hs-CRP in mg/L (no upper limit applied).

DAPSA values will be categorized in the following disease activity states:

- Remission (REM) (DAPSA ≤ 4),
- Low Disease Activity (LDA) (DAPSA from >4 to ≤ 14),
- Medium Disease Activity (MDA) (DAPSA from >14 to ≤ 28),
- High Disease Activity (HAD) (DAPSA >28).

For analyses with imputation of missing data, the imputed value for DAPSA will be based on the imputed values for the individual components.

For OC analyses, if any individual component score is missing, the DAPSA score will be set to missing.

DAPSA state, DAPSA scores and changes in scores from Baseline will be analyzed at Week 4, 8, 12, and 16.

8.3.1.11 Change from Baseline in the Disease Activity Score -28 based on C-reactive protein (DAS28[CRP])

The components for DAS28[CRP] include:

- the TJC and SJC based on 28 joints ([Section 8.1.1.1](#)):
 - Upper extremity (26) - bilateral shoulders, elbows, wrists (includes radiocarpal, and carpal and carpometacarpal bones considered as a single unit), metacarpophalangeal joints I, II, III, IV, and V, thumb interphalangeals, proximal interphalangeal II, III, IV, and V.

- Lower extremity (2) - knees.
- the PGA-Arthritis (ranging from 0 to 10 by dividing the original value by 10)
- the hs-CRP (in mg/L)

DAS28[CRP] is calculated as follows:

$$DAS28[CRP] = 0.56 \times \sqrt{TJC} + 0.28 \times \sqrt{SJC} + 0.014 \times PGA - Arthritis + 0.36 \times \ln(hs - CRP + 1) + 0.96$$

For analyses with imputation of missing data, the imputed value for DAS28[CRP] will be based on the imputed values for the individual components.

For OC analyses, if any individual component score is missing, then the DAS28 [CRP] score will be set to missing.

The changes from Baseline in DAS28[CRP] will be analyzed at Week 4, 8, 12, and 16.

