 - If (Q3 =0 or missing) and Q1 = missing, then Q3=missing.
- Hours actually worked:
 - If Q1 = NO, then Q4 = missing.
 - If (Q4 =0 or missing) and Q1 = missing, then Q4=missing.
- Work productivity:
 - If Q1 = NO, then Q5 = missing.
 - If (Q5 =0 or missing) and Q1 = missing, then Q5=missing.
 - If Q4=0, then Q5 = missing.

In the listings, the original values will be kept and displayed.

WPAI-SHP scores are based on 1-item (presenteeism, activity impairment), 2-items (absenteeism) and multiple items (overall work productivity). A score cannot be calculated if there is a missing response to the corresponding item.

A negative number will indicate a reduction in the score/improvement for subjects.

The change from Baseline score is derived as post Baseline score minus Baseline score. A negative change score indicates a reduction in the score/improvement for the subject.

The change from Baseline in scores will be analyzed at Week 12 and 16.

The analysis of WPAI-SHP scores will be performed on OC only.

8.3.1.23 Responses to the EuroQol-5D-3-Level (EQ-5D-3L) dimensions, change from Baseline in VAS score

The Euro-Quality of Life 5-Dimensions 3 Level (EQ-5D-3L) version health questionnaire provides a descriptive profile and a single index value for health status (using a VAS).

The instrument is composed of a 5-item health status measure (mobility, self-care, usual activities, pain/discomfort, anxiety/depression) and a VAS. Each of the 5 health states is divided into 3 levels (no problem, some or moderate problems, and extreme problems) and is scored as 1, 2, and 3, respectively. These scores are referred as “utility scores”.

The EQ-5D VAS records the respondent's self-rated health status on a vertical 20 cm visual analogue scale, graduated from 0 to 100 (0=worst imaginable health status, 100=best imaginable health status).

The response in each of the 5 items of the EQ-5D-3L and the values and the changes in VAS from Baseline will be presented at Week 4, 12, and 16.

8.3.1.24 Change from Baseline in Patient's Global Assessment of Arthritis (PGA-arthritis) and Physician's Global Assessment of Arthritis (PhGA-Arthritis)

The physician's global assessment of arthritis (PhGA-Arthritis) and the patient's global assessment of arthritis (PGA-Arthritis) are clinical outcomes based on visual analog scales (VAS) ranged from 0 to 100 (in mm).

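### DAS28[CRP] divides the patient global by 10 and then weights it 0.014, so that component can move the score by at most 0.14; weight and scale appear mismatched

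*SAP*

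**What the plan says.** Section 8.3.1.11 lists four inputs to DAS28[CRP]: "the TJC and SJC based on 28 joints" (two inputs), "the PGA-Arthritis (ranging from 0 to 10 by dividing the original value by 10") and "the hs-CRP (in mg/L"). The score is the sum of 0.56 × √TJC, 0.28 × √SJC, "0.014 \times PGA - Arthritis", 0.36 × ln(hs-CRP + 1) and a constant of 0.96.

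Section 8.3.1.24 describes PGA-Arthritis as collected on "visual analog scales (VAS) ranged from 0 to 100 (in mm"). The table of non-composite continuous endpoints in Section 4.2.1 gives it the same 0–100 range. The division by 10 is therefore made when the score is derived, not when the data are collected.

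The preceding section, 8.3.1.10 on DAPSA, uses the same rescaling: "PGA-Arthritis represents the patient's global assessment of arthritis ranging from 0 to 10; 0=best, 10=worst". There the rescaled value is added to the sum with no coefficient.

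On use: "The changes from Baseline in DAS28[CRP] will be analyzed at Week 4, 8, 12, and 16". Section 2.2.3.1 lists the score among the other efficacy variables. No section qualifies the rescaling.

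**The concern.** A coefficient in a composite score means something only together with the unit it multiplies. Here the unit has been made ten times coarser while the coefficient is a small one, and the result is a named component with very little influence. The identical division in DAPSA, one section earlier, serves an unweighted sum, where a 0–10 range is sensible. Carry-over of that instruction into DAS28[CRP] is a plausible explanation, though the SAP cannot prove it.

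A programmer following the text would apply it literally. Nothing in the SAP, such as a stated score range, a category cut-off or a citation, would reveal a tenfold scale error. Every reported DAS28[CRP] value and change would then down-weight the patient global tenfold relative to the collected scale, and would not be comparable with a DAS28[CRP] computed on the other scaling.

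**Working it through.** The SAP states no range or contribution for this score, so there is no figure of its own to reproduce. The check evaluates the formula directly.

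**Inputs.** Weights 0.56, 0.28, 0.014 and 0.36, 28 joints per count, and PGA divided by 10 (Section 8.3.1.11); collected PGA range 0–100 mm (Section 8.3.1.24).

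**Largest possible term for each bounded component**

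- TJC28: 0.56 × √28 = 2.96
- SJC28: 0.28 × √28 = 1.48
- PGA as written: 0.014 × 10 = 0.14
- PGA on the collected scale: 0.014 × 100 = 1.40

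The CRP term has no maximum, because Section 4.2.1 sets no upper limit for hs-CRP. For orientation, 0.36 × ln(hs-CRP + 1) is 0.70 at 6 mg/L, 0.86 at 10 mg/L and 1.66 at 100 mg/L.

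**Relative weight.** As written, the TJC28 maximum is 2.96/0.14 ≈ 21 times the PGA maximum, and the SJC28 maximum is 1.48/0.14 ≈ 11 times. On 0–100 the ratios are about 2.1 and 1.1. At maximum joint counts and maximum PGA, with hs-CRP assumed anywhere from 0.05 to 100 mg/L, PGA makes up 2.2–3.0% of the variable part of the score as written and about 19–24% on 0–100.

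**Effect on absolute values.** Per 10 mm of PGA, the term is 0.014 × 1 = 0.014 as written and 0.014 × 10 = 0.14 on 0–100, a gap of 0.126. At 60 mm the gap is 6 × 0.126 = 0.76; at 100 mm it is 1.26.

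**Effect on change from Baseline.** A 30 mm improvement contributes 0.014 × 3 = 0.042 as written and 0.014 × 30 = 0.42 on 0–100.

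**One illustrative subject** (all values assumed): TJC28 8 to 4, SJC28 5 to 2, hs-CRP 6 to 2 mg/L, PGA 60 to 20 mm.

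- Tender joints: 0.56 × (√4 − √8) = −0.464
- Swollen joints: 0.28 × (√2 − √5) = −0.230
- CRP: 0.36 × (ln 3 − ln 7) = −0.305
- PGA as written: 0.014 × (2 − 6) = −0.056, total −1.06 (PGA 5% of the change)
- PGA on 0–100: 0.014 × (20 − 60) = −0.56, total −1.56 (PGA 36% of the change)

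**Effect on the treatment difference.** If mean PGA improvement on bimekizumab exceeds that on placebo by *d* mm, the between-group difference in DAS28[CRP] change is smaller as written by (0.014 − 0.0014) × *d* = 0.0126*d*. With *d* = 10 that is 0.126; with *d* = 0 it is nil.

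**The case against.** The strongest reply is that the SAP does not contradict itself here. It gives one scale and one weight, and cites no source, range or threshold that the formula fails to meet. That the weight belongs with a 0–100 value is an inference from relative size, and composite scores can be very unequally weighted. In this SAP's PASDAS (Section 8.3.1.6), before the final multiplier, the tender-joint term reaches only 0.048 × ln 69 = 0.20 while the physician-global term reaches 0.18 × √100 = 1.8, about a ninefold gap. This stands as far as proof goes: low weight is suggestive, and the SAP cannot show whether the division or the coefficient is the slip. It does not remove the mismatch, which also rests on the same rescaling appearing in DAPSA, where it fits.

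The reply is also right to limit several readings that a reader might infer:

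- **A single joint outweighs the whole patient global.** One tender joint is worth 0.56 only when the count goes from 0 to 1, because the term is a square root. From 3 to 4 joints it is 0.56 × (2 − √3) = 0.15, and from 8 to 9 it is 0.096, so at such counts one joint is worth about the full 0.14 or less.
- **Any treatment difference is understated.** The formula does not imply this; the direction depends on which arm improves more on PGA.
- **The component is removed.** It is weighted down tenfold relative to the collected scale, not set to zero. PGA-Arthritis is also reported separately at Weeks 4, 8, 12 and 16 (Section 8.3.1.24).
- **A formal conclusion is at risk.** DAS28[CRP] is outside the testing sequence in Section 4.5 and the nominal p-value list in Section 8.3.2.3. It is summarised descriptively by visit under Section 8.3.2.2, and the SAP defines no DAS28[CRP] category, so no subject is misclassified.

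**Conclusion.** The point holds as a strong mismatch between weight and scale. The 0.14 ceiling follows exactly from the SAP's formula. That this is unintended is a judgement, resting on the size of the term and its likely origin in DAPSA; the document does not prove it or identify the wrong figure. If the 0–100 scale is the intended one, absolute values are too low by the amounts shown above, and nine tenths of each subject's patient-global change is missing from the DAS28[CRP] change. Any effect on the comparison between arms depends on the difference in PGA change, which the SAP does not give.

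It is worth correcting because it affects every reported DAS28[CRP] value at very little cost. Its reach is limited to one descriptive endpoint.

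**What to change.** Check the published source of the DAS28[CRP] formula for the unit of its patient-global term, and cite that source in Section 8.3.1.11. Then make weight and scale agree: apply 0.014 to PGA-Arthritis in 0–100 mm and drop the division by 10 in this section, or keep the 0–10 value with a weight of 0.14. The two give the same score. Leave the DAPSA rescaling in Section 8.3.1.10 as it is.

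Make the same change in the derivation program. The cost is one line in the SAP, one line of code and a rerun of the DAS28[CRP] summaries. If the source does pair 0.014 with a 0–10 value, a sentence saying so closes the point.

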8.3.1.12 Change from Baseline in all individual ACR core components

Individual ACR components (as listed in [Section 8.1.1](#)) are:

- SJC,
- TJC,
- HAQ-DI,
- PtAAP,
- PhGA-PsA,
- PGA-PsA,
- hs-CRP.

The change from Baseline (ratio from Baseline for hs-CRP) for each of the ACR components will be summarized at Week 4, 8, 12, and 16.

8.3.1.13 Enthesitis-free state based on the LEI and change in LEI from Baseline in the subgroup of subjects with enthesitis at Baseline

The Leeds Enthesitis Index (LEI) is an index composed of 6 items, 3 for the right part and 3 for the left part of the body that measures the severity of enthesitis. The body parts are lateral epicondyles of the humerus, medial femoral condyle, and Achilles tendons. Each item is scored for pain with either 1 (painful) or 0 (no pain). The total score ranges from 0 (no enthesitis) to 6 (severe enthesitis).

Note that LEI is collected for all subjects regardless of their Baseline score.

In case 4 items are missing, the LEI will be set to missing. If at least 3 items are available, the available items will be assessed and scored and then weighted by the number of the assessed items (AI) as shown in the formula below:

$$LEI = n \times \frac{\sum_{i=1}^n score}{\sum_{i=1}^n AI}$$

Note that n refers to the number of total items.

Enthesitis-free state is based on LEI of 0, for subjects with enthesitis at Baseline (LEI>0). Analyses on LEI will be restricted to the subset of subjects with enthesitis at Baseline (defined as LEI score>0).

The percentage of subjects with enthesitis free-state and the change from Baseline in LEI, in the subgroup of subjects with enthesitis at Baseline, will be analyzed at Week 4, 8, 12, and 16.

While not a secondary endpoint, to support the pooled endpoint in PA0010, enthesitis free-state at Week 16 will be analyzed using the same analysis method as the primary analysis.

8.3.1.14 Enthesitis-free state based on the SPARCC index and change in SPARCC index from Baseline in the subgroup of subjects with enthesitis at Baseline

The SPARCC index measures the severity of enthesitis through the assessment of 16 sites, 8 for the right part and 8 for the left part of the body: the greater trochanter (right/left), quadriceps tendon insertion into the patella (right/left), patellar ligament insertion into the patella and tibial tuberosity (right/left), achilles tendon insertion (right/left), plantar fascia insertion (right/left), medial and lateral epicondyles (right/left), and the supraspinatus insertion (right/left). Tenderness on examination is recorded as either present (1) or absent (0) for each of the 16 sites, for an overall score range of 0 (no enthesitis) to 16 (severe enthesitis).

In case 9 or more items are missing, the SPARCC index will be set to missing. If at least 8 items are available, the available items will be assessed and scored and then weighted by the number of the assessed items as shown in the formula below:

$$SPARCC\ index = n \times \frac{\sum_{i=1}^n score}{\sum_{i=1}^n AI}$$

where n refers to the number of total items, and AI the number of assessed items.

Analysis of the change of SPARCC index at Week 16 from Baseline will be restricted to the subset of subjects with enthesitis at Baseline (defined as SPARCC >0).

Enthesitis-free state based on SPARCC index is a status defined as subjects having achieved a SPARCC index score of 0 at Week 16. This endpoint represents the proportion of subjects with enthesitis at Baseline who achieve a SPARCC index score of 0 at Week 16.

The percentage of subjects with enthesitis free-state and the change from Baseline in the SPARCC index (on the subgroup of subjects with enthesitis at Baseline) will be analyzed at Week 4, 8, 12, and 16.

8.3.1.15 Dactylitis-free state based on the LDI and change in LDI from Baseline in the LDI in the subgroup of subjects with dactylitis at Baseline

The LDI measures the percent difference between the circumference of the affected digit and the circumference of the digit on the opposite hand or foot (referred to as the contralateral digit), where circumference is measured in millimeters. A minimum difference of 10% and the assessment of the investigator that the digit was affected by dactylitis will be used to define a dactylitis digit.

The percent difference between circumferences will be multiplied by a tenderness score (0 for the score using the binary tenderness non-tender, 1 for tender). This score using the binary tenderness score is referred to as the LDI basic. The results from each digit with dactylitis will then be summed to produce a final LDI score.

Table 8–4 provides the comparison, if matching digits are thought to be involved.

Table 8–4: Normative values for LDI

	Digit	Men	Women
Hand	Thumb	70	58
	Index	63	54
	Middle	63	54
	Ring	59	50
	Little	52	44
Foot	Great toe	82	72
	Second	52	46
	Middle	50	44
	Fourth	50	44
	Little	52	45

The following rules will be applied for the LDI calculation in case of unclear data.

- Circumferences of 0 will be considered as missing. Circumferences <15 will be assumed to be in cm instead of mm and will be multiplied by 10 before being used in summaries/analyses.
- If both digits of a given pair are recorded as affected, then each digit will be compared to the normative value (shown in the above table). Note that if both comparisons result in a difference $\geq 10\%$, then both digits will contribute to the final LDI score.
- If the circumference of the affected digit is smaller than the unaffected digit, then the LDI will be calculated by comparing the smaller digit to the normative value.
- If a digit is recorded as affected and the circumference of the contralateral digit is missing, the normative value will be used for comparison with the affected digit.
- If a digit is selected but recorded as ‘not affected’ but has circumference and contralateral circumferences collected, a missing tenderness score will be considered as 1.
- If the investigator did not complete the LDI questionnaire at Baseline, it will be assumed that no digits were affected (ie, a LDI score of 0 will be assigned).

Dactylitis-free state is based on a Leeds Dactylitis Index (LDI) of 0, for subjects with dactylitis at Baseline (LDI>0). Analyses will be restricted to the subset of subjects with dactylitis at Baseline (defined as LDI score>0).

Note: A tender dactylitis count will be calculated as the sum of the tenderness scores for all digits and will be used for the PASDAS score calculation (Section 8.3.1.6).

The percentage of subjects with dactylitis free-state and the change from Baseline in LDI (on the subgroup of subjects with dactylitis at Baseline) will be analyzed at Week 4, 8, 12, and 16.

While not a secondary endpoint, to support the pooled endpoint in PA0010, dactylitis free-state at Week 16 will be analyzed using the same analysis method as the primary analysis.

8.3.1.16 Change from Baseline in the Bath Ankylosing Spondylitis Disease Activity Index (BASDAI) in the subgroup of subjects with axial involvement defined by a score of ≥ 4 at Baseline

The BASDAI measures the disease activity of ankylosing spondylitis. The BASDAI is a validated self-reported instrument which consists of 6 horizontal NRSs, each with 10 units to measure the severity of the following 5 major symptoms over the last week: fatigue, spinal pain, peripheral joint pain and swelling, enthesitis, and morning stiffness (both severity and duration) over the last week.

To give each symptom equal weighting, the average of the 2 scores relating to morning stiffness is taken. The resulting 0 to 50 sum score is divided by 5 to give a final BASDAI score between 0 and 10, with lower scores indicating lower disease activity.

The BASDAI is calculated as follows:

$$BASDAI = \frac{Q1 + Q2 + Q3 + Q4 + \left(\frac{Q5 + Q6}{2}\right)}{5}$$

where Q1 – Q6 are the six questions from the BASDAI questionnaire.

If 1 of the 2 morning stiffness measurements (ie, questions: “How would you describe the overall level of morning stiffness you have had from the time you wake up?” and “How long does your morning stiffness last from the time you wake up?”) is missing, the other one will be used for the morning stiffness calculation.

If one major symptom of the BASDAI is missing, the total score of the remaining symptoms will be divided by the number of symptoms assessed. If more than one major symptom is missing, the total BASDAI score will be set to missing.

Analyses will be restricted to the subset of subjects with axial involvement at Baseline (defined as BASDAI score of ≥ 4).

Change from Baseline in BASDAI will be analyzed for subjects with axial involvement at Baseline (BASDAI ≥ 4) at Week 4, 8, 12, and 16.

8.3.1.17 Change from Baseline in the modified Nail Psoriasis Severity Index (mNAPSI) score at Week 4, 8, 12 and 16 in the subgroup of subjects with psoriatic nail disease at Baseline

Subjects with psoriatic nail disease will have a target nail selected at the Baseline Visit for evaluation using the mNAPSI. The nail selected should be the most affected nail observed at Baseline and should be the only one assessed throughout the study. The target nail will be scored (from 0 to 3) for onycholysis/oil drop dyschromia, nail plate crumbling, and pitting and will be

scored (0 for “no” or 1 for “yes”) for leukonychia, nail bed hyperkeratosis, splinter hemorrhages, and red spots in the lunula. The total score (also called the mNAPSI score) will then range from 0 to 13 with higher scores indicative of more severe nail disease.

If any of the 7 response items that contribute to mNAPSI is present, while other items are missing (ie, partial mNAPSI data), then the missing items are assumed to be 0 for the mNAPSI calculation. In some cases, the data may be captured in such a way that only non-zero component scores are present in the database. Again, those components that are not present are simply assumed to be 0 for the mNAPSI calculation

Analyses will be restricted to the subset of subjects with psoriatic nail disease at Baseline (defined as mNAPSI score>0).

Change from Baseline in mNAPSI and mNAPSI resolution (mNAPSI=0 at post-Baseline assessments) will be analyzed for subjects with psoriatic nail disease at Baseline (mNAPSI score>0) at Week 4, 8, 12, and 16.

